# **FUNDING**

Tennessee Clinical and Translational Science Institute, *Opioid Reduction for Total Knee Replacement Patients*. 2021-2020. Total costs: \$30,000.

# **PROJECT OVERVIEW**

### **Purpose**

The purpose of this work is to examine the efficacy of a brief intervention to reduce opioid use following total knee replacement.

We will conduct a randomized clinical trial to test our newly adapted Opioid Reduction Program ORP (vs. Treatment As Usual; TAU) for a population of patients presenting for Total Knee Replacement (TKR) surgery (N=100). Our intervention will include a discussion of the risks of opioid use, pain management through nonnarcotic medication and mindfulness techniques, and opioid weaning strategies that will assist patients with reductions in opioid use, even for those with chronic pain. We will assess outcomes using opioid refill requests, prescription drug monitoring, and pill counts of opioid medication at 4 weeks (short term follow up) and 12 weeks (long term follow up) following TKR surgery.

**Aim 1:** Examine the efficacy of our ORP vs. TAU control in reducing opioid use among TKR surgery patients. Opioid use following TKR surgery will be assessed via daily diaries, pill counts, medical chart review of prescription refills, and prescription drug monitoring for opioid refills from other physicians.

**Hypothesis 1**: We hypothesize that at 4 weeks, a higher percentage of those in the OPR group will express an intent to reduce future opioid medication use as compared with those in TAU.

**Hypothesis 2**: We hypothesize that those in the ORP will have lower cumulative exposure to opioid medication (i.e., morphine milligram equivalents [MMEs] at 12 weeks) than those in TAU.

Aim 2: Examine the relation between opioid use and TKR functional recovery following surgery.

**Hypothesis 3**: We predict that those who reduce their opioid use (as evidenced by fewer MMEs) will engage more in activities that will increase range of motion and functional knee use (e.g.,physical therapy and athome exercises), thereby increasing the speed of recovery.

### **Background**

According to the 2017 National Survey on Drug Use and Health data, 11.4 million Americans over age 12 reported the misuse of opioid medication in the past year, demonstrating that opiate misuse is a critical public health problem. Opioid misuse and use disorder are likely to develop from prescribed use. Evidence suggests that greater exposure (in terms of medication strength and length of use) is linearly related to risk of later misuse. Recent medical claims research indicates that among opioid naïve patients (N=536,767), those who fill opioid prescriptions 1 time are 2.9% more likely to become long term users (vs. non-opioid users), whereas those who fill 4 or more times are 26.1% more likely to use opioids long term. Further, continued exposure to opioids can produce hyperalgesia in some patients, lowering their pain threshold and leading them to crave more opioid analgesic.

When considering the risk of exposure, orthopedic surgery settings are a clear point of intervention. Orthopedic surgeries are associated with the prescribing of more opioids than any other surgical specialty,  particularly for total knee replacement surgery (TKR),  which is associated with severe post-operative pain.  Research suggests that this pain tends to last for extended periods in some patients; Significant pain (visual analog scale score of > 40) is reported by 44.4% of patients at 1 month post-surgery, 22.6% of patients at 3 months post-surgery, 18.4% of patients at 6 months post-surgery, and 13.1% of patients at 12 months post- surgery.  Management of this pain can lead to lengthy opioid exposure; Namba et al. found that of 24,105 TKR patients, 9,914 (41.5%) continued opioid use after 12 weeks.  Further, the population of individuals presenting for TKR surgery is increasing at an exponential rate,  and research indicates a need for increased communication between surgeons and patients regarding appropriate opioid analgesic use before and after surgery.  Research from other specialties suggests that surgery specific counseling can reduce functional recovery time and reliance on opioid analgesic,  although no studies have explored these outcomes in TKR patients.

### Rationale

In the context of prescribed opioids, research suggests that increased exposure is associated with long-term opioid use. Orthopedic surgeries are associated with the prescribing of more opioid narcotics than any other surgical specialty, particularly for Total Knee Replacement surgery, which is associated with severe post-operative pain. The proposed project is a randomized clinical trial to explore the efficacy of our Total Knee Replacement Opioid Reduction Program (ORP) vs. Treatment As Usual (TAU) in the reduction of opioid use following total knee replacement surgery.

#### **Intervention Content:**

- 1. Psychoeducation
- 2. Non narcotic pain management
- 3. Mindfulness

### **Population**

We will recruit a large sample of patients (N=100) who present for TKR surgery at Campbell Clinic. Participants must be 18 years of age or older.

# **Eligibility**

#### **Inclusion Criteria**

To be eligible to participate, participants must meet the following requirements:

- Presenting for a pre-operatory appointment at Campbell Clinic for TKR surgery that will result in the prescribing of opioid medication
- 18 years of age or older
- Have access to a telephone
- Be able to understand consent procedures

#### **Exclusion Criteria**

Those that exhibit any of the following will be ineligible to participate:

• Contraindication to opioid medications

# **Research Design**

This is a randomized, controlled clinical trial in which participants will be randomized 1:1 to one of two arms: TKR ORP intervention or treatment-as-usual (TAU).

Randomization will occur on a 1:1 ratio in blocks of 4.

#### **Outcome Measures**

Outcomes Aim 1: We will assess regular opioid use prior to and following surgery, using a daily diary of opioid medication use, opioid medication pill counts, information transcribed from the medical file (medication prescribed and prescription refill requests), and prescription drug monitoring data.

Outcomes Aim 2: We will assess functional recovery using the Knee Injury and Osteoarthritis Outcome Score. In addition to our main outcomes, we will assess potential confounders and moderators of treatment, including history of and current chronic pain, pain catastrophizing, opioid tolerance and craving, adverse events, knowledge about opioid risks prior to/following intervention, and transcribed surgical specifics from the medical file (analgesia, complications).

# **PROCEDURES**

#### Recruitment

Recruitment of participants will be done exclusively through Campbell Clinic. Potential participants will be identified by Drs. [name], [name], [name], [name], [name], and [name] (or their assistants) or study staff from the surgery schedule, which requires access to Campbell Clinic's electronic health record (ehr SRS). Remaining inclusion and exclusion criteria will be determined from a screening measure conducted prior to enrollment and randomization.

#### Recruitment Script

**Introduction**: Hi, My name is [Name] from the University of Tennessee Health Science Center. We are partnered with the Campbell Clinic to recruit patients into the TKR Study, a project where we talk to people about their medication following total knee replacement surgery. Your surgeon, [Surgeon's Name], is one of our partners, so I wanted to introduce myself to you and see if you'd be interested in learning more about a study for Total Knee Replacement patients.

**If they don't** seem interested: No worries, thank you for your time. If you change your mind, feel free to reach out to your doctor or [Doctor's Assistant's Name] anytime before your surgery. They can give you my information.

If they seem interested: Great! The TKR Study's goal is to test a behavioral treatment program in Total Knee Replacement surgery patients. The purpose is to educate patients on appropriate use of opiate pain medications. If you wanted to participate, you would need to complete 3 or 4 visits with us, depending on which group you are placed in. If you are in the control group (treatment as usual), you will just have 3 visits. The first visit is before your surgery and will take approximately 30 minutes. The last 2 visits will be 4 weeks and 12 weeks after your surgery, and they should take about 15 minutes to complete. The other group you could be placed in is the intervention group, which is the group that receives the counseling sessions for appropriate opioid use. If you are in that group, you will have an extra visit 2 weeks after your surgery. It shouldn't last longer than 20 minutes. These visits can be done after your scheduled visits at Campbell Clinic or they can be done over the phone, whichever is more convenient to you. There is no cost to you. We will compensate you for your time with electronic Amazon gift cards. If you complete the 1st visit, 4 week visit, and 12 week visit, you will receive a total of \$150 for your time.

Does this sound like something you'd like to do? (If **yes**: screen for eligibility and begin baseline visit procedures or schedule a baseline visit).

### **Cascade of Events**

#### **Baseline**

Contact potential participants prior to surgery to provide information about participation

- Screening for eligibility/exclusionary criteria
- Informed Consent
- Baseline assessments
  - Contact Information
  - Demographics
  - History of opioid use
  - Non-narcotic pain medication use
  - Knowledge pre-test
  - Quality and intensity of pain (SF-MPQ-2)
  - Short and long-term patient-relevant outcomes (KOOS JR)
  - Pain catastrophizing
- Randomization to Opioid Reduction Program (ORP) vs. Treatment As Usual (TAU; no intervention)
- ORP only:
  - For the experimental group:
    - ORP discussion including the following topics: risks of opioid use, tolerance and addiction, consequences of using opioids with alcohol or other sedatives, appropriate use of opioid medication, use of acetaminophen/ibuprofen in place of opioid, and appropriate disposal of opioid
- Provide incentive (Amazon gift card sent directly to participant's email, or ordered and printed for participant to take) for participation in visit 1
- Set appointment date/time for booster (ORP arm) or 4-week follow-up (TAU arm)

ORP only: Booster Session (In-person at Campbell Clinic or over-the-phone, 2wks post op)

Delivery of ORP booster intervention 2-weeks after surgery

4-Week Follow-Up (In-person at Campbell Clinic or over-the-phone)

- Assessment of: Opioid medication pill count and regimen (when taken, number of pills taken per
  dose), pain in the days following surgery, current pain, knowledge post-test, use of other pain
  management, and self-report of opioid takeback for disposal, opioid tolerance and craving, adverse
  events, opioid daily diary.
- Medical record abstraction including surgery specifics (analgesia, complications), functional recovery, and medication refills.
- Provide incentive for participation in follow-up (Amazon gift card sent directly to participant's email, or ordered and printed to mail to participant)

12-Week Follow-Up (In-person at Campbell Clinic or over-the-phone)

- Assessment of: Opioid medication pill count and regimen (when taken, number of pills taken per
  dose), pain in the days following surgery, current pain, knowledge post-test, use of other pain
  management, and self-report of opioid takeback for disposal, opioid tolerance and craving, adverse
  events, opioid daily diary.
- Medical record abstraction including medication refills and functional recovery.
- Provide incentive for participation in follow-up (Amazon gift card sent directly to participant's email, or ordered and printed to mail to participant)

#### **Baseline Visit**

Prior to surgery, interested patients will be assessed for inclusion/exclusion criteria. Those who are eligible will be consented prior to participation. After consent, we will collect baseline measures, and participants will be randomized. Those randomized to the intervention arm will receive the intervention during this visit.

Please see the measures section to review which measures are used during the Baseline visit.

# **Screening**

Eligibility will be determined by both chart review and self-report. Potential participants will be informed about the general overview of the study. If the patient expresses interest in the study, the Eligibility Questionnaire will then be administered to determine eligibility. (This can also be done at the beginning of a scheduled Baseline Visit before consent).

#### **Informed Consent**

The consent of the subject will be obtained at the first study visit at the participant's physician visit. If inperson is not possible, informed consent can also be done over-the-phone using either Docusign (digital signature) or by mailing the potential participant the current consent form. Please note if mailing: the participant's surgery date should be more than 2 weeks out to give adequate time for it to reach the participant and return to us.

Inviting the subject to read and sign the consent form is not sufficient for securing informed consent. Study staff will explain the nature of the study and answer all questions regarding the study. A copy of the informed consent will be given to the subject, and the original(s) will be placed in the subjects' research record. An entry documenting informed consent must also be made in the subjects' research record to confirm that informed consent was obtained prior to any study-related procedures and that the subject received a signed copy. The objection of any subject in word or action to the performance of study procedures will be sufficient for their withdrawal or exclusion from the study.

#### Illiterate English Speaking Subjects Procedures (from the IRB):

- 1. Potential subjects who are mentally competent and understand English, but who do not read or write English (i.e., are illiterate), may be enrolled in research studies by making or placing an "X" on the consent document in the space for the participant signature after the study information has been reviewed with them.
- 2. Upon verbal explanation, the potential subject should be able to: a. describe the study procedures in lay terms and appreciate what will be involved in participation in the study, b. understand the risk(s) and benefit(s) of being in the study, and c. indicate approval or disapproval regarding participation in the study.

- 3. The person obtaining the consent should ascertain the above and document in the research record the method(s) utilized to communicate with the subject and the method(s) utilized by the subject to communicate agreement to enter the study.
- 4. A signed copy of the informed consent document shall be given to the subject or his or her legally authorized representative.
- 5. Video and audiotaping of the process may be utilized with permission of the individual and in accordance with the institution's policies.

Study procedures will not continue until a signed consent form is received. Please note: if the consent is done by mail, we cannot do any study procedures or collect information until we receive the signed consent form back in the mail.

If a participant decides NOT to consent, the process will immediately be stopped, and the consent form will be voided. The participant will be given an ID number in the database, classified as "Did Not Consent", and no information will be stored except for their MRN number.

#### **Profile Information & Assessments**

After informed consent is complete, the next step is to collect profile information within the database. This includes information such as:

- Participant's first/last name
- Phone number
- Mailing address
- Email
- Best method of contact
- Alternate Contact
- Surgery date
- Etc.

After filling out all the necessary profile information, select "create visit checklist" in the database, and it should take you to the questionnaires for Visit 1 (Baseline). The assessments should now be administered, starting with demographics and ending with the knowledge pre-test. Once each measure is complete, you will notice the box in the database turns a different color to reflect that. With that being said, do not click on questionnaires in future visits, as this will mess up the database, and there is no way to reverse it.

# Randomization

Randomization happens during the Baseline Visit, after all the assessments are complete. *Please note that randomization and treatment (ORP) must occur during the same visit*. The randomization scheme is as follows:

CTSI-TKR is a prospective randomized clinical trial with two treatment arms (n = 50 each for a total of 100 participants): Opioid Reduction Program (ORP) and Treatment As Usual (TAU). Participants are individually

assigned to a study arm by stratified variable-block randomization (randomly chosen block-lengths of 4 or 6 and separate sequences in each of the two strata defined by sex/gender).

The randomization scheme was determined by the statistician and can be found under the "Study Management" folder. Within the randomization log, simply locate the appropriate tab (according to your participant's gender) and find the next blank, which will tell you if that person is in ORP group (intervention) or TAU group (control). Make sure to fill out the study ID number, date of BV, and transfer the allocID to the participant's database profile.

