### Scheduling Script for BV

What days/times are you usually available? We're usually available Monday-Friday from 8am-4:30pm. (Find a time before their surgery that works for both of you.) Great! I'll get you on the calendar for your first visit on DAY at TIME. (Let them know if you or someone else will be the one calling them.) You will need to

have access to your email/computer or smart phone for this visit so you can sign our electronic consent form. Do you have any questions or concerns about this visit? (Answer any questions they may have.) Thanks again for your interest in the TKR Study. We look forward to speaking with you again soon. Have a great day!

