# STUDY DOCUMENTATION

## **OneDrive & Filemaker**

#### **OneDrive**

All study forms (e.g. the consent form, study measures, the regulatory binder, this MOP, the randomization list, etc.) are kept on OneDrive. In order to access the TKR OneDrive folder, permission will need to be granted (i.e. the folder will need to be shared to each person's UT email).

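### Enrolling staff read each arm from a shared randomization log with no step that conceals later rows, and the protocol states two different block schemes

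*Protocol*

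**What the plan says.** Under Randomization (Protocol), the arm is obtained at the baseline visit once the assessments are done. Staff open the log, go to the tab for the participant's gender and "find the next blank, which will tell you if that person is in ORP group (intervention) or TAU group (control". They then enter the study ID and visit date themselves.

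On storage, the OneDrive section says: "All study forms (e.g. the consent form, study measures, the regulatory binder, this MOP, the randomization list, etc.) are kept on OneDrive". On access it says: "In order to access the TKR OneDrive folder, permission will need to be granted", meaning that the folder is shared to each person's university email.

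The same study staff can be involved earlier. Under Recruitment, candidates may be found by the surgeons, their assistants or "study staff from the surgery schedule". The Recruitment Script has the recruiter "screen for eligibility and begin baseline visit procedures or schedule a baseline visit" as soon as the patient agrees. The baseline scheduling script adds "Let them know if you or someone else will be the one calling them", so the person who books the visit may also conduct it.

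The block scheme is described twice. Research Design says: "Randomization will occur on a 1:1 ratio in blocks of 4", with no strata. Randomization says: "randomly chosen block-lengths of 4 or 6 and separate sequences in each of the two strata defined by sex/gender". The SAP mentions neither blocks nor strata.

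**The concern.** Random allocation protects against selection only if the people deciding whom to approach, and when to book the visit, cannot foresee the next arm. Here the arm is already in the log before the participant's row is filled in, and enrolling staff are directed to that log. The folder permission keeps outsiders away but not the enrolling staff, who need access to do their job.

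A recruiter who knows or can guess the next arm may, even without intending it, approach a different patient or change the order of visits. Randomizing after consent and baseline assessments fixes when the arm is formally read. It does not stop anyone looking ahead before approaching or booking. The SAP's balance check and covariate adjustment deal with measured factors only, and the intent-to-treat analysis keeps participants in the arm they were given. Neither restores concealment.

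The block conflict matters because readers cannot tell which scheme was used, or whether the analysis should reflect stratification by sex.

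A lesser point concerns follow-up. The follow-up sections require blinded assessors, but no safeguard is described that keeps them away from the list or from the database profile into which the allocation ID is copied.

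**Working it through.** **Inputs.** From the protocol: 100 participants, 1:1 allocation, and the two block schemes above. Assumed, because the documents do not say: sex splits from 50:50 to 30:70, block lengths 4 and 6 equally likely, and an observer who knows every past assignment. The last is plausible for enrolling staff, since the intervention must be given at the same visit as randomization.

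**The plan's own figure.** 100 × 1/2 = 50 per arm, as the Randomization section states.

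**Later rows readable.** Every assignment is known beforehand, 100 of 100, whatever the block scheme.

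**Later rows hidden, fixed blocks of 4.** With *a* and *b* places left for the two arms in the current block, the next assignment is certain if *a* = 0 or *b* = 0. The best guess is right with probability max(*a*, *b*)/(*a* + *b*).

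- Certain: among the 6 orderings of AABB, AABB and BBAA each have 2 determined positions and the other four have 1 each. That is 2×2 + 4×1 = 8 of 24 positions, or 33.3%.
- Best guess, positions 1 to 4: 1/2, 2/3, (1/3)×1 + (2/3)×(1/2) = 2/3, and 1. The mean is (1/2 + 2/3 + 2/3 + 1)/4 = 17/24, or 70.8%.

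**Later rows hidden, blocks of 4 or 6 by sex.** The block position is not known for sure, so the observer carries a probability *w* for each possible state (*a*, *b*), updated by Bayes' rule after each assignment. Then P(next is A) = Σ *w*·*a*/(*a* + *b*). The assignment is certain if this is 0 or 1, and otherwise the likelier arm is guessed (ties count one half). This was simulated with 5,000 lists per sex split; Monte Carlo standard errors are 0.05 (certain) and 0.02 (correct). The fixed-4-by-sex row used 3,000 lists.

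| Situation | Certain per 100 | Correct per 100 |
|---|---|---|
| Pure chance | 0 | 50 |
| Later rows readable, either scheme | 100 | 100 |
| Hidden, fixed 4, single sequence | 33.3 | 70.8 |
| Hidden, fixed 4 by sex, 50:50 | 31.9 | 70.4 |
| Hidden, 4 or 6 by sex, 50:50 | 5.56 | 69.04 |
| Hidden, 4 or 6 by sex, 40:60 | 5.58 | 68.99 |
| Hidden, 4 or 6 by sex, 30:70 | 5.53 | 69.01 |

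A separate simulation of single strata of 30, 50 and 70 gave 5.5 to 5.7 certain and 68.8 to 69.1 correct.

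**Reading the table.** Hiding later rows takes correct guesses from 100 to about 69 to 71. The choice of block scheme moves them by 70.8 − 69.0 = 1.8, or by 70.4 − 69.0 = 1.4 with both schemes split by sex. It moves certain assignments far more, from 33.3 to about 5.6.

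**The case against.** The strongest reply is that the harm is inferred. The protocol says only that the next blank shows the arm. The log itself is not reproduced, subfolder permissions are not described, and the Study Team and Study Staff pages listed in the contents were not in the text reviewed. On this view, all the documents establish is that a concealment mechanism is not described, and the figure of 100 known assignments holds only if later rows can be read. This stands as a limit on what can be claimed. It does not remove the gap: the instructions do specify how assignment works, and followed exactly they contain no concealing step.

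Second, recruiter and randomizer may be different people. Surgeons' assistants can identify candidates, and someone else may run the booked visit. That is true, but the text equally allows one person to do everything.

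Third, there is little room to manipulate. Candidates come from the surgery schedule, there is one exclusion criterion, the baseline visit must precede surgery, and a recruitment call log is kept. These features narrow the route without closing it. Guess counts are also not a measure of bias, and the 69 to 71 assumes an ideal observer.

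Fourth, if later rows are in fact hidden, the block conflict is not trivial, because certain assignments differ about sixfold between the schemes (33.3/5.6 ≈ 6). This is fair. Variable blocks offer useful protection in that case, which is a further reason to state which scheme applies.

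**Conclusion.** The point holds. The assignment procedure gives enrolling staff a shared log with the arms already in it and describes nothing that keeps upcoming rows from them. Confidence is medium, because the log's layout and any undocumented access limits are unknown.

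If later rows can be read, foreknowledge is complete. If they cannot, predictability with full knowledge of past assignments is about 69 to 71 in 100, under the stated assumptions on sex split and block lengths. What this does to the treatment comparison, in size or direction, cannot be worked out from the documents.

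Concealment is the main issue. The disagreement between Research Design and Randomization is a plain contradiction in current text and mainly a documentation error. Assessor access to the list or to arm-revealing records is secondary, since it is not known whether the allocation ID discloses the arm.

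**What to change.** 1. The statistician keeps the list outside the shared folder, with no access for anyone who recruits, enrols or assesses.
2. Assignments are released singly, only after consent and baseline assessments are logged. A database function could return one row, or sequentially numbered opaque envelopes could be kept separately by sex. Because visits may be by telephone, any envelopes need a named holder who does not recruit or assess.
3. The Randomization section is reworded so that staff enter the study ID and sex, receive one time-stamped assignment, and never open the list.
4. Follow-up assessors are kept from the list, from any database field that reveals the arm, and from booster-session records.
5. Research Design and Randomization are reconciled to the scheme actually used.
6. If enrolment has begun, the team records and reports who has had access to the log.

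The cost is small: one file moved, permissions changed, and a simple release step added. The documents do not show whether the FileMaker database can release single assignments, so that needs checking; envelopes are the alternative. The baseline visit gains a short extra step. A backup release route is needed because randomization and the intervention must take place in the same visit. No extra participants are required.
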